5. INFORMED CONSENT

Informed consent will be taken at the beginning of the baseline visit. It is the responsibility of the Principal Investigator (PI), or a suitably trained delegate, to obtain informed consent for each patient prior to performing any trial related procedures. This task can be delegated by the PI to other suitably trained members of the local research team, if local practice allows and this responsibility has been documented in the site signature and delegation log. Consent will be taken face to face on a paper consent form at research sites.

A Participant Information Sheet (PIS) will be provided when the patient is invited to take part in the trial, which will give them sufficient time to read it and discuss their participation with others outside of the site research team prior to consent. The PI, or delegate, will ensure that they adequately explain the aim of the trial, the trial intervention, and the anticipated benefits and potential hazards of taking part in the trial to the patient. They will also explain that participation is voluntary and that the patient is free to decide to take part and may withdraw from the trial at any time.

The patient will be given the opportunity to ask questions before signing and dating the current approved version of the Informed Consent Form (ICF). The PI or delegate will then sign and date the ICF. A copy of the ICF will be given to the participant, a copy will be filed in the medical notes and the original placed in the Investigator Site File (ISF). Once the patient is randomised into the trial, the participant's trial number will be entered on the ICF maintained in the ISF. As part of the consent process, the patient is asked to give their permission for a copy of the signed ICF to be transferred to the trial team at BCTU for review.

Details of the informed consent discussions will be recorded in the patient's medical notes. This will include date of discussion, the name of the trial, summary of discussion, version number of the PIS given to participant, version number of ICF signed and date consent received. Where consent is obtained on the same day that the trial related assessments are due to start, a note should be made in the medical notes as to what time the consent was obtained and what time the procedures started.

At each visit the participant's willingness to continue in the trial will be ascertained and documented in the medical notes. Throughout the trial the participant will have the opportunity to ask questions about the trial. Where new information becomes available which may affect the participants' decision to continue, participants will be given time to consider and if happy to continue they will be re-consented. Re-consent will be documented in the medical notes. The participant's right to withdraw from the trial will remain.

Electronic copies of the PIS and ICF will be available from the Trial Office and will be printed or photocopied onto the headed paper of the local institution.

6. INCLUSION/EXCLUSION CRITERIA

At the baseline visit, all potentially eligible patients will have their eligibility assessed against the following criteria:

6.1 Inclusion criteria

1. COPD diagnosis confirmed by post-bronchodilator spirometry ($FEV_1/FVC < 0.7$), any GOLD stage
2. Current daily smoker
3. Willing to try to stop smoking using only allocated trial products
4. Aged 35 or over

6.2 Exclusion criteria

1. Unable to perform spirometry to a satisfactory standard (e.g. due to dementia, lack of teeth, lack of coordination or not having a good oral seal)
2. Deemed as unsuitable to participate in the trial (e.g. terminal illness, unable to give informed consent)
3. Unable to participate in behaviour support calls
4. Severe angina or unstable cardiovascular disease (CVD)
5. History of end stage kidney disease
6. History of cirrhosis of the liver
7. Currently taking part in another trial of smoking cessation or COPD treatment/management
8. Contraindications to spirometry within the last 12 weeks – tuberculosis infection, cardiac infarction, retinal detachment, Pneumothorax or surgery on the chest, abdomen, brain, ears or eyes (*invite back and re-assess after 12 weeks*)

This will be undertaken by an appropriate member of site staff, delegated this responsibility on the ECAL Site Signature and Delegation Log. In some circumstances it is appropriate to have someone other than a qualified medical doctor assess eligibility. We have conducted a risk assessment and as the safety profile of the IMP is established as low risk and patients will not be put at any higher risk of side effects from either intervention than standard care, and the inclusion and exclusion criteria are straightforward, it is appropriate that eligibility can be delegated to an appropriately trained member of site staff overseen by a medically qualified doctor. Prior to randomisation, the eligibility of each trial participants will be confirmed by a delegated and suitably trained medically qualified doctor at site; confirmation of eligibility will be documented on the baseline assessment visit CRF prior to randomisation.

Details of all patients screened for trial will be recorded on the ECAL Participant Screening/Enrolment Log which will be kept in the ISF and should be available to be sent to the Trials Office upon request.

6.3 Co-enrolment

Potentially eligible patients who are already taking part in another trial for the treatment/management for COPD or smoking cessation will be excluded (this is an exclusion criteria). Similarly, ECAL participants will be made aware that they are not allowed to take part in any other trials for the treatment/management for COPD or smoking cessation.

The Trial Management Group (TMG) will consider requests for co-enrolment into other trials not related to COPD or smoking cessation in accordance with best practice recommendations. This will ensure careful consideration of patient burden, compatibility of interventions, organisational issues and follow-up.

7. RANDOMISATION and BLINDING

7.1 Randomisation process

After informed consent has been received, eligibility has been confirmed, and baseline assessments have been completed, the participant can be randomised into the trial using the REDCap trial database (see section 10.3 for baseline procedures).

Randomisation will be provided via the trial database using a secure online system (available at <https://bctu-redcap.bham.ac.uk>), thereby ensuring allocation concealment. Unique log-in usernames and passwords will be provided to those who wish to use the online system and who

have been delegated the role of randomising participants into the trial as detailed on the ECAL Site Signature and Delegation Log. These unique log-in details must not be shared with other staff and in no circumstances should staff at sites access either system using another person's login details. The online system will be available 24 hours a day, 7 days a week, apart from short periods of scheduled maintenance which sites will be informed of in advance.

In the event of the online system not being available, a back-up telephone toll-free randomisation service ([name]) is available Monday to Friday, 09:00 to 17:00 UK time, except for bank holidays, government guided closures and University of Birmingham closed days.

Participants will be randomised at the level of the individual in a 1:1 ratio to either the intervention (EC) or comparator (NRT). A minimisation algorithm will be used within the online randomisation system to ensure balance in the treatment allocation over the following key potential confounding variables:

- COPD stage (levels: stage 1-2 and stage 3- 4 based on FEV₁)
- Age (levels: 35-65, 66+ years)
- Sex at birth (levels: male, female)
- Fagerstrom test for nicotine dependence (FTND) score (levels: ≤6, 7+)

To avoid the possibility of the intervention allocation becoming predictable, a random element will be included in the algorithm. Full details of the randomisation specification will be stored in a confidential document at BCTU.

Participants randomised by error, i.e. randomised twice or found ineligible according to inclusion/exclusion criteria after randomisation, will be replaced to attain the full sample size.

Following randomisation, a confirmatory e-mail will be sent to the local PI, research nurse/delegated person who randomised the participant. The trial team will also receive a randomisation confirmatory e-mail.

The local research team should add the participant to the ECAL Participant Recruitment and Identification Log which links patients with their Trial Number. PIs must maintain this document securely and it must not be submitted to the Trial Office. The ECAL Participant Recruitment and Identification Log should be held in strict confidence.

7.2 Blinding

This is an open-label trial and trial participants, care providers, investigators and outcome assessors will not be blinded to treatment allocation. This is because it is not possible to blind given the physical nature of the interventions. However, the primary outcome measure is validated using an objective measure (exhaled CO).

7.3 Informing the participant's GP and other parties

Patients will give explicit consent for their General Practitioner (GP) to be notified of their participation in the trial.

The participant's GP will be notified using the ECAL GP notification letter/ email, which will be sent directly from the randomising site. The GP notification letter/ email will include the name of the trial, the participant's randomised intervention allocation and also advise the GP to monitor their patient whilst they try to quit smoking.

As part of the trial risk protocol, the GP of participants who are identified as at risk (i.e., a HADS scoring of ≥ 11 and/or disclosure of other mental health related issues of concern) may need to be informed of this by letter/ email.

No other parties outside of the trial team will be informed of the participant's entry into the trial.

8. TRIAL INTERVENTION

8.1 Trial interventions and dosing schedule

Intervention arm: Electronic Cigarettes (EC) - Participants will receive an EC starter pack and an initial supply of e-liquid to start using the e-cigarette (up to 20 mg nicotine/ml). Participants will be advised on how to continue sourcing further supplies themselves from reputable vendors in their preferred nicotine strength and flavours. Participants in the intervention arm will be offered weekly telephone behavioural support up to 4 weeks post quit.

Comparator arm: Combination Nicotine Replacement Therapy (NRT) - Participants will receive up to 12-week supply of a nicotine patch plus a fast-acting nicotine product to be used in combination. A pragmatic approach to product allocation will allow for variation based on participant preference and availability. Participants who do not wish to use patches (e.g. due to previous experience of skin irritation) will be offered two types of fast acting product. Participants in the comparator arm will also be offered weekly telephone behavioural support up to 4 weeks post quit.

8.1.1 Telephone behavioural support

All participants will be advised at the baseline visit that they will receive six weekly behavioural support telephone calls from stop smoking advisors which will commence within a few days of the baseline visit. These will be delivered by the Health and Lifestyle Research Unit at the Wolfson Institute of Population Health at Queen Mary University of London (QMUL). During these calls, the advisor will deliver behavioural support according to the National Centre for Smoking Cessation Training Standard Programme⁴⁴ including setting a TQD and providing further support around medication use. The TQD will be set for approximately 2 weeks after the baseline visit. Should participants have already started their quit attempt at the first phone call, the -1 week and TQD behavioural support phone calls will be combined. If participants are unable to be contacted to set a TQD then a default TQD will be set (approximately 2 weeks after the baseline visit) for follow up time points to be based on.

8.2 Drug interaction or contraindications

8.2.1 Permitted medications/interventions (including rescue medication)

There are no known contraindications for NRT or ECs and no clinically relevant interactions between NRT and other drugs. For cautions see British National Formulary (BNF)/Summary of Product characteristics (SmPC).

8.2.2 Concomitant medications/interventions

Concomitant medications will be continued as per the participant's usual care plan.

8.2.3 Prohibited medication(s)/intervention(s)

There are no prohibited medications for participants whilst they are participating in this trial.

8.3 Intervention modification or discontinuation

In the main PIS, at the baseline visit and/or during the behavioural support phone calls, participants will be informed about potential side effects of combination NRT use and about

different e-liquid nicotine strength. Should participants experience side effects, they will be advised during behavioural support telephone calls to reduce their dose of nicotine/day.

If participants decide to discontinue use of combination NRT or ECs, this will be captured during the behavioural support telephone call and documented on a CRF. Discontinuation of use will not mean the participant has withdrawn (see section 10.11). Participants who want to continue with their quit attempt using a product not allocated to them as part of the trial will be advised to contact their local stop smoking service.

8.4 Continuation of intervention after the trial

[figure not shown]
No further EC refills or NRT will be provided after participation in the trial has ended. Any continuation of ECs or NRT will be at the participant's expense and is not required for the trial.

8.5 Intervention supply and storage

8.5.1 *Intervention supplies*

All NRT products used within the trial will be classed as General Sales List medicines and will be used within their Marketing Authorisation (MA). The risk assessment has determined that there is no requirement for a prescription as these products are available to purchase from any shop without any supervision from a pharmacist or healthcare professional. Participants will indicate their choice of product(s) to be ordered, at the baseline visit (after randomisation) and during the behavioural support telephone calls (for any further supplies ordered). Allocated product orders will be sent to the central stop smoking service who will coordinate these being dispensed by a central pharmacy to participants through the post. At a minimum, sites should order an amount of NRT at the baseline visit to allow participants to start their quit attempt, and further supplies up of to 12 weeks will be made available to participant as identified at the behavioural support telephone calls. Product dispensing will depend on participants' choice and availability.

Note: The e-cigarette (EC) is not an Investigational Medicinal Product (IMP) in this trial as it is a consumer product regulated under the Tobacco and Related Product Regulations. The trial team will work with the central stop smoking service to coordinate the distribution of an EC starter pack to participants, but participants will be permitted to purchase a different EC device and/or e-liquid if the one provided does not work for them. E-cigarette start packs and e-liquid will be supplied from reputable vendors.

8.5.2 Packaging and labelling

There are no special packaging requirements for the IMP (NRT products) being used in the comparator arm, as this is an open-label RCT. Drug accountability and trial specific labelling will not be required due to Regulation 46 exemption.

There are no special labelling requirements for the EC starter kits as these are consumer products and this is an open label RCT.

8.5.3 NRT storage

NRT stock will be stored within the central pharmacy in line with product data sheets. Products will be supplied to participants as per the central pharmacy’s SOPs.

8.5.4 Storage deviations

The IMP (NRT products) can normally be purchased over the counter. The central pharmacy will store products in accordance with product data sheets. Any storage deviations will be handled in line with the central pharmacy’s policies.

8.5.5 *IMP recalls*

In the event that a trial product is recalled by the manufacturer, the central pharmacy who dispensed the products will be responsible. The central pharmacy will follow local their recall SOP and participants should be advised to contact the manufacturer if required.

8.6 Accountability

Drug accountability to allow traceability will be according to the central pharmacy's supply SOP. Participants will also be asked to self-report trial product use at the behavioural support telephone calls (1-, 2-, 3- and 4-weeks post TQD), at the 26 weeks follow up phone call and at the 52 week follow up visit.

8.7 Adherence

Adherence to trial products will be monitored through the behavioural support calls and at follow time points. All participants will be asked to self-report their use of allocated products.

9. OUTCOME MEASURES

N.B. all follow up points referred to in outcome measures for main trial, economic analysis and sub studies are calculated from the target quit day.

9.1 Internal pilot outcomes

The outcome of the internal pilot is progression to full trial (yes, no), and if yes, are any changes required. Decisions will be made based on pre-defined STOP-GO criteria (table 2 - traffic light criteria). The STOP-GO criteria will be assessed at 5 months post-start of recruitment.

Table 2 – Traffic light criteria

Green	Number of participants recruited: $\geq 100\%$
	Number of sites actively recruiting: 15
	Withdrawal from the trial due to unacceptability of ECs: $< 20\%$

If all three criteria are met; continue the trial with protocol unchanged (unless there is clear indication from our experience that would improve the protocol).

Amber	Number of participants recruited: 51-99%
	Number of sites actively recruiting: 7-14
	Withdrawal from the trial due to unacceptability of ECs: 20-49%

If one or more of the amber criteria are met, then the trial will need review to see what changes (if any) could be made to improve whichever criteria are not at the 'green' level before proceeding to the full trial.

Red	Number of participants recruited: $\leq 50\%$
	Number of sites actively recruiting: < 7
	Withdrawal from the trial due to unacceptability of ECs: $\geq 50\%$

If one or more of the red criteria are met, we will discuss with the Trial Steering Committee (TSC) and the funder regarding feasibility of the trial continuing and contingency plans.

The definitions of the factors used in the stop-go criteria are:

- **Participants recruited:** The participants recruited will be calculated as a percentage. This will be the number of participants recruited in month 4 and 5 divided by the number of expected based on the number of open sites in month 4 and 5.
For example, if we are successful in opening 20 sites during the pilot phase by month 4 as we are planning, we expect to recruit 160 participants during months 4 and 5 (Target monthly recruiting target = 4 patients/month/research site).
- **Number of sites actively recruiting:** An actively recruiting site is one that has been trained and is open to recruitment.
- **Complete withdrawal due to unacceptability of ECs:** Participants who ask to withdraw from the trial because being randomised to ECs is not acceptable.

At the end of the pilot phase, the TMG will prepare a report on trial progress for the independent TSC. There will also be an assessment of safety by the Data Monitoring Committee (DMC). Based on the traffic light criteria above and confirmation from the DMC that there are no safety issues to prevent the trial from continuing, the TSC will recommend if the RCT should continue or not.

9.2 Main trial outcomes

9.2.1 Primary outcome

Abstinence from smoking since TQD biochemically validated (exhaled CO < 8 ppm) at 52 weeks post TQD, defined in accordance with the Russell Standard¹

9.2.2 Secondary outcomes

1. Abstinence from smoking for at least 26 weeks biochemically validated (exhaled CO < 8 ppm) at 52 weeks
2. 7-day point prevalence abstinence from smoking biochemically validated (exhaled CO < 8 ppm) at 52 weeks
3. Self-reported abstinence from smoking for at least 26 weeks at 52 weeks

-
4. Self-reported 7-day point prevalence abstinence from smoking at 4, 26 and 52 weeks
 5. Reduction in cigarettes smoked (self-report of any and > 50% reduction from baseline to 52 weeks, confirmed by reductions in expired CO readings at 52 weeks)
 6. Reduction in cigarettes smoked (self-report of any and > 50% reduction from baseline to 26/52 weeks)
 7. Continued use of allocated product at 4, 26 and 52 weeks
 8. Withdrawal symptoms and urges to smoke (change from baseline to 1/ 2/ 3/ 4 weeks) measured using the mood and physical symptom scale (MPSS)
 9. COPD Symptoms (change from baseline to 4/ 26/ 52 weeks) measured using COPD Assessment Test (CAT) and the Clinical COPD Questionnaire (CCQ)
 10. Number of COPD exacerbations over the past 52 weeks (from baseline to 52 weeks)
 11. Number of self-reported upper respiratory tract infections over the past 52 weeks (from baseline to 52 weeks)
 12. Post bronchodilator spirometry (FEV₁, FVC and MMEF change from baseline to 52 weeks)
 - Forced Expiratory Volume in 1 Second (FEV₁): The maximal volume of air that can be expired in the first second of a forced expiration from a position of full inspiration (measured in Litres (L) and also expressed as the % predicted for age, sex, height and race)
 - Forced Vital Capacity (FVC): The maximal volume of air that can be expired during a forced and complete expiration from a position of full inspiration (measured in L and % predicted)
 - Mean Mid-Expiratory Flow (MMEF): The average flow between 25% and 75% of the FVC manoeuvre (measured in L/sec and % predicted)

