10.10 Collection and management of blood samples

Ideally between 36-45ml of blood will be collected from each participant at baseline and again at the 52 weeks follow up visit at the research sites. One EDTA tube will be used to conduct full blood following standard protocols. The remaining blood will be centrifuged for plasma/serum collection and storage. Samples will be maintained at -80 °C at the research sites. Sites unable to maintain samples at -80 °C may hold samples temporarily at -20 °C before shipping to the primary site (University of Birmingham Research Laboratories, Queen Elizabeth Hospital, Birmingham (QEHB)). Samples will be shipped to the primary site as capacity and storage conditions demands.

All samples will be shipped in a temperature-controlled environment on dry ice. Blood samples from participants who self-report quitting smoking and not vaping (quitters) or switching to exclusive e-cigarette use (vaping) will be sent to a contracted external laboratory to test cotinine levels. For participants who meet the inclusion criteria for the cohort analysis (based on smoking and vaping status) blood will be analysed for biomarkers and toxicants at the University of Birmingham or will be transported to contracted external laboratories for analysis.

Table 3: Schedule of Assessments

Visit	Identification of participants/ Pre-baseline assessment	Baseline	-1w pre TDQ	Target Quit day (TQD) + 3 days	+1 week post TQD ± 3 days	+2 week post TQD ± 3 days	+3 week post TQD ± 3 days	+4 week post TQD ± 14 days	26 week post TQD + 30 days	52 week post TQD + 100 days
Eligibility check	X	X								
Valid informed consent		X								
Concomitant medication check		X								
Relevant medical history taken		X								
Randomisation		X								
Dispensing of IMP (EC or Combination NRT)		X								
Behavioural support			X	X	X	X	X	X		
Instructions to patient about the trial		X								
Blood sample		X								X
Spirometry		X								X
Exhaled CO measurement		X								X
Baseline questionnaire*		X								
Behavioural support session questionnaire**								X		X
Follow up questionnaire***									X	X

*Baseline questionnaire includes the following validated questionnaires: COPD assessment test (CAT), Hospital anxiety and Depression Scale (HADS), Clinical COPD Questionnaire (CCQ) for measuring COPD symptoms., EQ-5D-5L for measuring quality of life for the economic evaluation., Fagerstrom Test for Nicotine Dependence (FTND).

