**Behavioural support session questionnaire (at 4 weeks) includes the following questionnaires: Mood and physical symptom score (MPSS) for measuring nicotine withdrawal symptoms, COPD assessment test (CAT), Clinical COPD Questionnaire (CCQ) for measuring COPD symptoms and EQ-5D-5L† for measuring quality of life for the economic evaluation.

***Follow up questionnaire includes the following validated questionnaires: COPD assessment test (CAT) – 26w and 52w, Clinical COPD Questionnaire (CCQ) for measuring COPD symptoms - 26w and 52w, EQ-5D-5L for measuring quality of life for the economic evaluation – 26w and 52w, and Hospital anxiety and Depression Scale (HADS) – 52w only .

† Validated for delivery over the telephone

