12.3 Participant completed questionnaires

Participant completed questionnaires can be completed in clinic, during behavioural support calls or via postal paper questionnaires.

Participants will complete a questionnaire at baseline, +4 weeks behavioural support telephone call, 26 weeks and 52 weeks after TQD. The following validated questionnaires will also be used as an assessment of health and quality of life for patients with COPD:

- Mood and physical symptom score (MPSS) for measuring nicotine withdrawal symptoms.
- COPD assessment test (CAT).
- Hospital anxiety and Depression Scale (HADS)
- Clinical COPD Questionnaire (CCQ) for measuring COPD symptoms.
- EQ-5D-5L for measuring quality of life for the economic evaluation.
- Fagerström Test for Nicotine Dependence (FTND)

A bespoke resource use questionnaire developed from existing COPD resource use questionnaires will be completed at 26-week and 52-week for the economic evaluation.

Baseline and 52-week questionnaires will be completed on paper. Data collected on paper forms will then be transcribed onto the REDCap data capture system by a delegated member of site staff or the Trial Office. If for any reason a Baseline or 52-week questionnaire has not been completed during the clinic visit, an MDC questionnaire will be collected via post and transcribed into the REDCap database.

Participant questionnaires at +4 weeks behavioural support telephone call and 26 week follow up can be completed by telephone with the support of the smoking cessation advisor. If necessary, an MDC 4+ week or 26-week questionnaire will be sent via post to a participant for completion.

If completed in clinic, the questionnaire should be completed by the participant alone but physical assistance in completing the form can be given by site staff or the participant's friends and relatives where appropriate. In such circumstances, questions are to be read to the participant verbatim and the responses must not be led by the person assisting with the completion. This requirement should be made clear when the participant's friends and relatives are helping.

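### MPSS is not scheduled at baseline or at weeks 1, 2 and 3, although secondary outcome 8 is MPSS change from baseline to each of weeks 1 to 4

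*Protocol*

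**What the plan says.** **The outcome.** Section 9.2.2, item 8, reads "Withdrawal symptoms and urges to smoke (change from baseline to 1/ 2/ 3/ 4 weeks"), measured with the MPSS. The Trial Summary and Appendix 1 define it the same way.

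**The model.** Section 15.2.2 analyses continuous secondary outcomes with a repeated measures mixed-effects model. It adjusts for the baseline score and includes every assessment time after randomisation.

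**The schedule.** The footnotes to Table 3 (in section 10.10) list the instruments in each questionnaire:

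- Baseline: "Baseline questionnaire includes the following validated questionnaires: COPD assessment test (CAT), Hospital anxiety and Depression Scale (HADS), Clinical COPD Questionnaire (CCQ"), followed by EQ-5D-5L and, last, "Fagerstrom Test for Nicotine Dependence (FTND"). MPSS is not in the list.
- Behavioural support sessions: "Behavioural support session questionnaire (at 4 weeks) includes the following questionnaires: Mood and physical symptom score (MPSS) for measuring nicotine withdrawal symptoms", together with CAT, CCQ and EQ-5D-5L.
- Weeks 26 and 52: "Follow up questionnaire includes the following validated questionnaires: COPD assessment test (CAT"), then CCQ, EQ-5D-5L and HADS. MPSS is not in the list.

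**Questionnaire times.** Section 12.3 states "Participants will complete a questionnaire at baseline, +4 weeks behavioural support telephone call, 26 weeks and 52 weeks after TQD". It then names MPSS in a general list of instruments without giving it a time point.

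**The concern.** The outcome list and the schedule of assessments do not agree. A change from baseline needs a baseline value, and a course over weeks 1 to 4 needs a value at each of those weeks. The protocol promises both, but its itemised schedule places MPSS only at week 4.

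The baseline gap matters most. The outcome is meant to show how withdrawal and urges move once the participant tries to stop, so its reference value has to be taken before the quit attempt. If sites follow the schedule as written, that value is lost for good for everyone already past the baseline visit. Scores for weeks 1 to 3 are likewise lost for anyone already past those calls. The SAP cannot repair this, because which instrument is collected at which visit is protocol content.

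**Working it through.** The protocol states no figure to reproduce here. The check sets what the outcome needs beside what the schedule assigns.

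**Needed** (section 9.2.2 item 8; section 15.2.2): MPSS at baseline and at weeks 1, 2, 3 and 4.

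| MPSS time point | Needed for | Assigned in the protocol? |
|---|---|---|
| Baseline | all four change scores; model covariate | No: not in the Table 3 baseline footnote |
| Week 1 | change to week 1 | No: no questionnaire at this time in section 12.3 |
| Week 2 | change to week 2 | No: as above |
| Week 3 | change to week 3 | No: as above |
| Week 4 | change to week 4 | Yes: Table 3 footnote on the 4-week questionnaire |

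**Counts.**

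- Measurements needed: 1 baseline + 4 post-quit = 5. Assigned: 1. Not assigned: 5 − 1 = 4.
- Change score at week *w* = MPSS(*w*) − MPSS(baseline). Needed: 4. Computable from assigned measurements: 0, because each one uses the unassigned baseline.
- Post-quit times for the model: 4 needed, 1 assigned, 3 unassigned. The baseline covariate is unassigned as well.

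**Other places that might fill the gap.**

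- *The general list in section 12.3.* Reading it as applying at every listed time would put the FTND at 26 and 52 weeks too, which the Table 3 footnotes do not do. Even on that reading, weeks 1 to 3 are absent, because section 12.3 has no questionnaire then.
- *The −1 week call.* It takes place after randomisation, and section 10.4 allows that a participant may already have started the quit attempt by then. It is not a clean baseline.
- *The Table 3 grid.* In the copy reviewed, the row for the behavioural support session questionnaire also carries a mark at week 52. This may be a layout fault. It supplies neither a baseline nor a value for weeks 1 to 3. The check relies on the footnotes and section 12.3, not on the grid.

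**The case against.** The strongest reply is that Table 3 is not a complete list of what is collected. Section 8.6 has product use self-reported at the 1-, 2-, 3- and 4-week calls, and section 11.3 has adverse events recorded at the behavioural support calls; neither has a row in Table 3. Section 10.4 says that call data go on purpose-built CRFs. Table 8 lists a baseline visit form, a pre-quit form and a form for weeks 1 to 3, and section 12.2 says that the list of forms is not exhaustive. MPSS may already be on some of them.

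This stands. A reader might infer that the outcome cannot be computed at all, or that MPSS is never collected before week 4. The documents do not support that, because the contents of the CRFs are not shown. They do support the statement that the protocol does not schedule these measurements. The reply also leaves the contradiction in place: no section puts MPSS at baseline or at weeks 1 to 3, and the one questionnaire said to contain it is tied to week 4.

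A second reply is that the impact is limited. This stands too. A week-4 comparison by randomised arm needs no baseline score to be unbiased; baseline adjustment adds precision. What is at risk is the change score and the early time course, for one of 12 secondary outcomes.

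A reader might also suppose that weeks 1 to 3 are when the two products differ most. The protocol does not say so, and the point does not depend on it.

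**Conclusion.** The point holds as an internal inconsistency that is wrong as written and should be fixed. From the scheduled measurements (1 of 5), none of the 4 change scores in secondary outcome 8 can be formed and the section 15.2.2 model lacks its baseline covariate. A week-4 comparison by arm is all that remains.

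The conclusion assumes that the itemised footnotes to Table 3 and the times in section 12.3 describe what is collected. If the baseline CRF and the weekly call CRFs already carry MPSS, the fault is one of wording and no data are lost. If they do not, the missing pre-quit scores cannot be recovered.

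The primary outcome and the sample size are unaffected. Nothing here bears on the validity of the main comparison, so the point does not rank with faults that threaten the trial's principal result.

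**What to change.** 1. Check the baseline, pre-quit and weekly call CRFs for MPSS.
2. If MPSS is absent, add it to the baseline questionnaire, to be completed before randomisation, and to the +1, +2 and +3 week call CRFs. Amend Table 3, its footnotes and section 12.3 to match.
3. If MPSS is already on those forms, state this in the same three places.
4. For participants without a baseline MPSS, compare by arm whichever post-quit scores were collected (at least week 4), adjusted for the minimisation variables and without a change score. Do not assume that week 1 to 3 scores exist for anyone who passed those calls before the change.

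**Cost.** The baseline visit and the three calls already take place, so the burden is a slightly longer visit and slightly longer calls, plus a protocol amendment. If the forms already hold MPSS, the cost is a wording correction.
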